4.2.2.3. EQ-5D-5L

The EQ-5D-5L is a validated quality of life questionnaire developed by the EuroQol group in order to provide a simple, generic utility measure for characterizing current health states of patients. It consists of 2 parts, the descriptive system and the visual analogue scale (VAS).

EQ-5D-5L descriptive system comprises 5 dimensions: mobility, self-care, usual activities, pain/discomfort, and anxiety/depression. Each dimension has 5 levels (no problems, slight problems, moderate problems, severe problems and extreme problems). EQ-5D-5L health states, defined by the EQ-5D-5L descriptive system, will be converted into a single index value according to the U.S. population (van Hout et al, 2012). The VAS records the respondent's self-rated health status on a vertical visual analogue scale. The VAS 'thermometer' has 100 (best imaginable health state) at the top and 0 (worst imaginable health state) at the bottom.

The actual value and change from baseline before initiating a new antineoplastic therapy will be summarized using descriptive statistics over time for EQ-5D-5L health states and VAS.

EQ-5D-5L analyses will be summarized by treatment arm among Ph3-ITT, Ph3-PP, and Ph2-ITT populations. For exploratory purpose, EQ-5D-5L will also be summarized in Ph3-OL and

Ph2-OL populations, in which changes from baseline will be calculated using baseline values for the open-label period, i.e., last assessment on or before the start of open-label treatment.

4.2.2.4. ORR

ORR is defined as the proportion of patients who achieve an ICR-determined best overall response of PR or CR per RECIST v.1.1, before ICR-confirmed PD or initiating a new antineoplastic therapy. Open-label selinexor is considered a new antineoplastic therapy for the purpose of assessing ORR for blinded study treatment.

The number and percentage of patients achieving PR or CR will be summarized by treatment arm among Ph3-ITT and Ph2-ITT populations respectively.

4.2.2.5. Time to Next Treatment (TTNT)

[figure not shown]
TTNT is defined as time since randomization until the first new antineoplastic therapy or death due to any cause, whichever occurs first. For patients without an event, their follow-up time will be censored at the date of discontinuation from the study, or date of last participating visit (e.g., a telephone contact with patient status being alive) on or before database cut-off date, whichever occurs first.

TTNT on patient's last prior systemic therapy is defined as time since start of last prior systemic therapy to start of blinded study treatment or death due to any cause, whichever occurs first. For patients who were randomized but never received study treatment, and did not die before discontinuation from study, their follow-up time will be censored at the date of discontinuation from the study, or date of last participating visit (e.g., a telephone contact with patient status being alive) on or before database cut-off date, whichever occurs first.

[figure not shown]
The analysis comparing TTNT on study treatment vs. on last prior systemic therapy will be conducted among patients in the Ph3-ITT population randomized to selinexor and placebo arms separately. To account for within-person correlation, a stratified Cox proportional hazards model analysis will be conducted stratifying on patient IDs. KM median TTNT times with 95% CIs, and KM curves will be provided.

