7.5.2.2. Secondary Efficacy Endpoints

- TTP, defined as the time from randomization to date of PD or death due to disease progression, whichever is earlier, per RECIST v. 1.1. Patients who remain progression free (whether they withdrew from the study or reached their maximum follow-up) will be censored at the date of their last disease assessment.
- ORR, defined as the proportion of patients who achieve complete response (CR) or partial response (PR), per RECIST v. 1.1.
- DOR, defined as the time from first occurrence of CR or PR until the first date of PD per RECIST v. 1.1 or death.
- Tumor glucose metabolism, density, and size using FDG-PET (Phase 2 only) and CT (diagnostic) after 6 weeks of treatment.
- PFS according to the Investigator, defined as the time from date of randomization until the first date of PD, per RECIST v. 1.1, or death due to any cause as defined by the Investigator based on clinical and/or radiologic criteria.
- Time to next treatment (TTNT), defined as the duration of time from randomization to the date of the next anti-cancer therapy.

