1. OVERVIEW AND INVESTIGATIONAL PLAN

1.1. STUDY DESIGN

This is a Phase 2-3, multicenter, randomized, double-blind, placebo-controlled study. Approximately 334 total patients were planned to be enrolled. At the conclusion of enrollment, three hundred and forty-two (342) patients have been randomized (57 patients in Phase 2 and 285 patients in Phase 3).

The study overview is presented in the figure below.

Patients in the placebo arm who have PD will have the option to cross over to open-label selinexor.

Phase 2:

Fifty-seven patients were randomized to selinexor or placebo in a 1:1 allocation. Randomization was stratified based on the following stratification factors for patients enrolled under protocol Versions ≤ 4 : number of prior systemic therapies (1 versus ≥ 2) and prior eribulin use (prior eribulin versus no prior eribulin). The preplanned analysis of progression-free survival (PFS; after 40 PFS events were observed) was performed and served as a guideline to inform the final design of the Phase 3 portion of the study.

Phase 3:

Two hundred and eighty-five (285) patients have been randomized to selinexor or placebo in a 2:1 allocation.

Randomization was based on

- Prior eribulin use (prior eribulin versus no prior eribulin)
- Prior trabectedin (Yondelis[®]) use (prior trabectedin versus no prior trabectedin)
- The number of prior systemic therapies excluding eribulin and trabectedin (≤ 2 versus ≥ 3).

All radiographic responses will be determined by the Independent Centralized Review (see the *Imaging Manual* for more details). Patients who have progressive disease (PD) per Response Evaluation Criteria in Solid Tumors (RECIST) v. 1.1 ([Eisenhauer 2009](#)) per central review, will discontinue blinded study treatment and their treatment assignment will be unblinded.

- Patients in the placebo arm who have PD will have the option to cross over to open-label selinexor.
- Patients in the selinexor arm who have PD will only be allowed to continue on selinexor (as open-label treatment) if the Investigator, in consultation with the Sponsor, believes based on clinical judgement that the patient may derive benefit from continued treatment with selinexor.

Patients who discontinue blinded study treatment at the discretion of the Investigator for reasons other than centrally confirmed PD are not allowed to receive open-label selinexor.

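### The within-patient TTNT comparison uses two clocks that do not measure the same event; its bias can run either way, and the never-dosed rule can count only against study treatment.

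*SAP*

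**What the plan says.** SAP 4.2.2.5 defines the on-study endpoint thus: "TTNT is defined as time since randomization until the first new antineoplastic therapy or death due to any cause, whichever occurs first". For the last prior line, the interval is "time since start of last prior systemic therapy to start of blinded study treatment or death due to any cause, whichever occurs first".

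A special rule covers patients with no dose: "For patients who were randomized but never received study treatment, and did not die before discontinuation from study", the prior-line clock is censored at study discontinuation or last contact. By implication, a never-dosed patient who dies has that death as the prior-line event.

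The comparison is stated thus: "The analysis comparing TTNT on study treatment vs. on last prior systemic therapy will be conducted among patients in the Ph3-ITT population", with the two arms taken separately, and "a stratified Cox proportional hazards model analysis will be conducted stratifying on patient IDs".

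Protocol 7.5.2.2 has no death component: "Time to next treatment (TTNT), defined as the duration of time from randomization to the date of the next anti-cancer therapy". The visible text of SAP 1.7 and 1.8 does not list the addition of death. Part of 1.7 is blacked out, so nothing more than that can be said.

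No hypothesis, alpha or sidedness is stated for this comparison. It lies outside the testing procedure in SAP 4.4. SAP 4.2 asks for caution with nominal secondary p-values, but the reason it gives is multiplicity.

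**The concern.** A Cox model stratified on patient, with two records per patient, only counts which of the two clocks ended first in each informative pair. It is a fair comparison only if the two times would be exchangeable within a patient when treatment makes no difference. Two features break this.

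First, every patient in Ph3-ITT was alive at randomization. For a dosed patient the words about death on the prior-line clock are empty: that clock always ends at study drug. On the study clock every death before a new therapy is an event.

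Second, for a never-dosed patient the prior-line clock continues past randomization, ignores any other therapy actually started, and covers the same calendar time as the study clock.

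The stake is a secondary hazard ratio, one per arm, that may be read as showing how long patients stayed off further therapy compared with their previous line. Part of what it shows is mortality and selection into the trial.

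**Working it through.** The plan states no alpha, effect size or death share for this comparison, so there is no figure to reproduce.

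**Inputs.** "Two hundred and eighty-five (285) patients have been randomized to selinexor or placebo in a 2:1 allocation" (SAP 1.1) gives 285 × 2/3 = 190 selinexor pairs and 285 / 3 = 95 placebo pairs. The protocol's 30 months of accrual plus 4 months gives study follow-up of about 4 to 34 months. Assumed, because the documents do not give them: constant therapy hazard L and death hazard M on study; q = M/(L+M), the share of study-side events that are deaths; a two-sided 5% test, so 2.5% per direction; and, in the simulations, a median time to next therapy of 6 months.

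**Test.** Let b be the pairs with the study event first and a the pairs with the prior-line event first. Then HR = b/a and z = (b − a)/√(a + b).

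**First null: the prior time seen in enrolled patients has the same distribution as study time to next therapy (rate L).** The study composite has rate L+M, so

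P(study first) = (L+M)/(2L+M) = 1/(2−q), and HR = 1/(1−q).

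Expected z is √n × q/(2−q). With n = 190 and q = 0.20 this is 13.78 × 0.20/1.80 = 1.53, against a threshold of 1.96, which gives rejection in about one trial in three. Simulation (4,000 trials per cell, study side censored uniformly over 4 to 34 months), study declared shorter:

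| q | HR = 1/(1−q) | 190 pairs | 95 pairs |
|---|---|---|---|
| 0 | 1.00 | 2.6% | 2.3% |
| 0.05 | 1.05 | 5.4% | 4.3% |
| 0.10 | 1.11 | 10.3% | 7.4% |
| 0.20 | 1.25 | 32.8% | 18.8% |
| 0.30 | 1.43 | 65.8% | 40.2% |

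The closed form without censoring agrees for 190 pairs: 5.4%, 10.8%, 33.5% and 68.6% at q = 0.05 to 0.30. At q = 0.20, medians of 3 or 12 months or a shared frailty of variance 0.5 give 28% to 35%.

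**Second null: both lines have the same L and M, and only survivors of the prior line can enrol.** Given that therapy came before death, prior time has rate L+M, which is the rate of the study composite. So P(study first) = 1/2 and HR = 1. Simulation gives 2.2% to 2.8% declared shorter at every q.

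If deaths are censored on the study side under this null, the study rate is L against L+M, so HR = L/(L+M) = 1−q. Study TTNT is then falsely declared longer in 5.0%, 9.8%, 30.4% and 60.0% of trials at q = 0.05, 0.10, 0.20 and 0.30 (190 pairs).

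**Non-constant death hazard under the second null (190 pairs, deaths as events).** A falling hazard (Weibull shape 0.7; death shares 18%, 28%, 37%) declares study shorter in 7.3%, 15.9% and 22.5%. A rising hazard (shape 1.5; shares 4%, 12%, 22%) declares study longer in 3.5%, 7.2% and 15.4%.

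**Unequal death hazards with survivor selection.** Take q = 0.30 and a study-line death hazard twice that of the prior line. In units of L+M the prior rate is 0.70 + 0.15 = 0.85, so HR = 1/0.85 = 1.18, although the therapy hazards are identical. Study is declared shorter in about 20% of trials with 190 pairs.

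**Never-dosed patients.** Let G > 0 be the time from the start of the last prior therapy to randomization.

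- Study time ends at new therapy, death or last contact.
- Prior time equals G plus the time from randomization to death or last contact, so it is always longer than study time.
- If a study event occurs, the pair adds to b. If none occurs, both clocks are censored and the pair is uninformative. Such a pair can never add to a.

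With an assumed 3% never dosed, all with a study event, and the other pairs evenly split: b = 0.485 + 0.03 = 0.515, a = 0.485, HR = 1.06.

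**The case against.** The strongest reply is survivor selection. Patients reached randomization only by surviving the prior line, so their prior times are already shortened, much as counting death shortens study times. With equal constant hazards the two effects cancel exactly and the SAP composite keeps its level. That stands, and it rules out calling the analysis biased in one known direction. It does not rescue the analysis, because the cancellation needs death hazards that are equal on both lines and constant over time.

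A reader might infer that death cannot occur on the prior-line side, that the test always finds study TTNT shorter, and that it does so far more often than 5%. The documents do not support this. The SAP names death on the prior line, and it is possible for never-dosed patients. Direction and size depend on q and on selection; at q = 0.05 the excess is small under either null. In the placebo arm q would be lower if open-label selinexor counts as a new therapy. SAP Table 4-1 and 4.2.2.4 say so for PFS and ORR, but 4.2.2.5 is silent for TTNT.

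It is also fair that no error rate is formally controlled here, since any p-value would be nominal. The caution in SAP 4.2 does not cover this problem, however: multiplicity is a different matter from clocks that are not comparable.

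**Conclusion.** The two clocks are not comparable, and the patient-stratified hazard ratio cannot be read as an effect on time to next treatment. For dosed patients this follows from the definitions alone. The size does not: under the first null it runs from negligible at q near 0 to an apparent HR of 1.43 at q = 0.30, under the second null with constant hazards it is nil, and with a rising death hazard it reverses. All these figures rest on the assumed q, hazards and 5% two-sided level.

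The never-dosed rule is wrong whatever null is chosen, but its effect is about 6% on the hazard ratio at an assumed 3% of patients and less if fewer are never dosed. The difference from protocol 7.5.2.2 needs only to be reconciled and listed.

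The comparison is secondary and outside the alpha hierarchy, so the primary and key secondary conclusions are untouched. The change is worth making because it needs no new data.

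**What to change.** In SAP 4.2.2.5, for the within-patient comparison:

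1. End the prior-line clock at randomization, counted as an event, for every Ph3-ITT patient, and delete the never-dosed rule. Alternatively, leave never-dosed patients out of the paired comparison. Either way the clocks should not overlap.
2. Reconcile the TTNT event with protocol 7.5.2.2 and list the change in SAP 1.7.
3. Report the hazard ratio as descriptive, without a p-value. Show beside it the number of deaths before next therapy and the cumulative incidence of next therapy, with death as a competing event.

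Do not replace the analysis with a test that censors deaths: under equal hazards on both lines that gives HR = 1−q, an apparent benefit that is not there.

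The cost is SAP wording and some reprogramming of dates and displays. The trial loses a nominal p-value for this comparison, and for never-dosed patients randomization stands in for the start of the next line.

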4.3. EXPLORATORY ENDPOINTS

CCI

CCI

[figure not shown]

4.4. MULTIPLE COMPARISONS/MULTIPLICITY

The overall type I error for the primary endpoint and each key secondary endpoint is strictly controlled at 0.025 (one-sided).

The graphical multiple testing procedure in Bretz et al (2009) will be used to test the primary and key secondary endpoints. It is a Bonferroni-based closed test procedure, so it strongly controls the family-wise error rate across the endpoints. See the figure below for the alpha reallocation for the primary and key secondary endpoints.

Figure 4-1: Graphical illustration of the propagation of endpoint-specific alpha

To account for the interim analysis with options to stop for futility (non-binding) or efficacy, type I error is adjusted using the Lan DeMets (Lan and DeMets, 1983) alpha spending function with the O'Brien-Fleming type of boundary. If the interim analysis is conducted for the unblinded sample size re-estimation, the overall type I error for the final analysis of the primary efficacy PFS endpoint will be maintained using the CHW method (Cui et al, 1999) (see Section 1.5).

Statistical significance of key secondary endpoints will not be claimed until the primary endpoint of PFS have reached significance. The key secondary endpoints will be tested using the hierarchical testing procedure as shown in Figure 4-1 to maintain the overall type I error.

5. SAFETY

Safety analyses will be reported by the actual treatment arm patients received and overall, among the Ph3-SAF and Ph2-SAF populations respectively. Unless otherwise specified, only data from the blinded treatment period will be presented. Please refer to Section 2.4 on definitions of observation periods.

For patients in the Ph3-OL and Ph2-OL populations respectively, selected safety data from the open-label period will be presented in separate summaries.

Safety analyses will be based on the reported AEs and other safety information, such as 12-lead electrocardiogram (ECG), vital signs, physical examination, ECOG performance status, clinical laboratory assessments including hematology and serum chemistry.

General rules

All safety analyses will be performed using the following common rules:

- Safety data in patients who do not belong to the safety population (e.g., enrolled but did not receive any dose of study treatment, partial or complete) will be listed separately.
- The baseline value is the last available value before first dose of study treatment. Please refer to Section 2.6 for details.
- The analyses of the safety variables will be essentially descriptive with no systematic testing planned.

5.1. ADVERSE EVENTS

An AE is defined as any untoward medical occurrence in a patient receiving a pharmaceutical product regardless of a causal relationship with this treatment. An AE can therefore be any unfavorable sign and unintended sign (including an abnormal laboratory finding), symptom, or disease temporarily associated with the use of a study treatment, whether or not related to the study treatment.

All AEs (including serious adverse events [SAEs]) will be coded to a preferred term (PT) and associated primary system organ class (SOC) using the MedDRA.

The severity of all AEs will be graded according to the NCI CTCAE Grading Scale, v. 4.03. An AE with a CTCAE grade of 3 or higher is considered a severe AE. The severity of the AE is different from the seriousness of the AE. For AEs not covered by CTCAE, the severity will be characterized as “mild,” “moderate,” “severe”, “life-threatening” (corresponding to Grades 1 to 4) according to the following definitions:

- Mild events are usually transient and do not interfere with the patient’s daily activities.
- Moderate events introduce a low level of inconvenience or concern to the patient and may interfere with daily activities.
- Severe events interrupt the patient’s usual daily activities.
- Life-threatening.

5.1.1. Definitions of Treatment-Emergent Adverse Events (TEAEs), Serious Adverse Events (SAEs), and Treatment-Emergent Treatment-Related Adverse Events (TRAEs)

5.1.1.1. Treatment-Emergent Adverse Event (TEAE)

For AE summaries for blinded treatment period, treatment-emergent adverse events (TEAEs) are defined as any event that developed or worsened or became serious during the blinded treatment period, i.e., from the date of first blinded study treatment up to the date of last blinded study treatment + 30 days inclusive (or the day before initiation of a new anti-neoplastic treatment, whichever occurs first), or if applicable, the date of first open-label study treatment exclusive, whichever occurs first. Please refer to Section 2.4 on definitions on observation periods. Additionally, TEAEs also include any event that developed post the blinded treatment period but was assessed by the Investigator as related to study treatment. Please note for few patients who were randomized to selinexor in blinded phase and entered open-label selinexor, their blinded study treatment period ends on the date of last non-zero dose of open-label selinexor + 30 days inclusive. To these patients, open-label selinexor is not considered a new anti-neoplastic therapy.

For AE summaries for the open-label period, TEAEs are defined as any event that developed or worsened or became serious during the open-label treatment period, i.e., from the date of first open-label study treatment up to the date of last open-label study treatment + 30 days inclusive (or the day before initiation of a new anti-neoplastic treatment, whichever occurs first).

Additionally, TEAEs also include any event that developed post the open-label treatment period but was assessed by the Investigator as related to open-label selinexor. This definition applies to Ph3-OL and Ph2-OL populations only.

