2.3. STUDY TREATMENT DOSING DATE

Study treatment dosing date is the date on which a patient actually received study treatment (selinexor or placebo, partial or complete).

For blinded treatment,

- Except for few patients who were randomized to selinexor in blinded treatment and entered open-label phase, the date of first study treatment is defined as the earliest date of non-zero dose of either selinexor or placebo. The date of last study treatment is defined as the latest date of non-zero dose of either selinexor or placebo before end of blinded treatment.
- For patients who were randomized to selinexor in blinded treatment and entered open-label phase, the date of first study treatment is defined as the earliest date of non-zero dose of selinexor, the date of last study treatment is defined as the latest date of non-zero dose of selinexor, regardless of blinded or open-label phase.

For open-label treatment, the date of first study treatment is defined as the earliest date of non-zero dose of open-label selinexor. The date of last study treatment is defined as the latest date of

non-zero dose of open-label selinexor. This definition only applies to patients who were randomized to placebo in blinded treatment and entered open-label phase.

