2.4. OBSERVATION PERIOD

For the patients who do not enter open-label selinexor, the observation period will be divided by the following:

- The pre-treatment period is defined as the time since the signed informed consent date up to the time before the date of first blinded study treatment.
- The blinded treatment period is defined as the time from the date of first blinded study treatment up to the date of last blinded study treatment + 30 days inclusive, or the day before initiation of a new anti-neoplastic treatment, whichever occurs first.
- The post-treatment period is defined as the time beyond the blinded treatment period.

For the patients who were randomized to placebo in blinded phase and entered open-label selinexor, the observation period will be divided by the following:

- The pre-treatment period is defined as the time since the signed informed consent date up to the time before the date of first blinded study treatment.
- The blinded treatment period is defined as the time from the date of first blinded study treatment up to the date of last blinded study treatment + 30 days inclusive, or the date of first open-label study treatment exclusive, whichever occurs first.
- The open-label treatment period is defined as the time since the date of first open-label study treatment to the date of last open-label study treatment + 30 days inclusive, (or the day before initiation of a new anti-neoplastic treatment, whichever occurs first).
- The post-treatment period is defined as the time beyond the open-label treatment period.

For the few patients who were randomized to selinexor in blinded phase and entered open-label selinexor, the observation period will be divided by the following:

- The pre-treatment period is defined as the time since the signed informed consent date up to the time before the date of first study treatment.
- The blinded treatment period is defined as the time from the date of first study treatment up to the date of last study treatment + 30 days inclusive, or the day before initiation of a new anti-neoplastic treatment, whichever occurs first. Please note that open-label selinexor is not considered a new anti-neoplastic treatment here.
- The post-treatment period is defined as the time beyond the blinded treatment period.

Please refer to Section 2.3 for the definitions of dates of first and last study treatment.

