3.1.2. Safety Populations

For evaluation of safety, the following safety populations are defined:

- The ***Phase 3 Safety Population (Ph3-SAF)*** will consist of all patients in Phase 3 who have received at least one dose of blinded study treatment.
- The ***Phase 2 Safety Population (Ph2-SAF)*** will consist of all patients in Phase 2 who have received at least one dose of blinded study treatment.

Patients in safety populations will be analyzed according to the actual treatment received.

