5.1.2. Analysis Methods

The primary focus of AE reporting will be on TEAEs.

If an AE date/time of onset (occurrence or worsening) is incomplete, an imputation algorithm will be used to determine the AE as treatment-emergent. The algorithm for imputing date/time of onset will be conservative and will classify an AE as treatment-emergent unless there is definitive information to determine it is not treatment emergent. Details on classification of AEs with missing or partial onset dates are provided in Section 2.2.2.

AE summaries will include number (n) and percentage (%) of patients who have experienced an AE. The denominator for computation of percentages is the number of patients in the corresponding treatment arm. Multiple occurrences of the same event in the same patient will be counted only once in the tables.

Unless otherwise specified, sorting order will follow the alphabetic order in SOC, and further by decreasing frequency of PTs within each SOC. When more than one PT has same number of events, the order of presentation will be alphabetical in PTs.

Based on the entries on the eCRF AE page, an AE is considered related to study treatment if the entry for “Relationship to study treatment” is “Related” or “Possibly Related”.

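### The related-event extension in the blinded TEAE definition has no crossover cut-off; read literally, it counts related events first arising on open-label selinexor as blinded-period events of placebo patients

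*SAP*

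**What the plan says.** SAP 5.1.1.1 defines the blinded-period TEAE in two steps. The base window runs from the first blinded dose to 30 days after the last. It is cut short by a new antineoplastic treatment or, where applicable, by the first open-label dose. A further sentence then says that "TEAEs also include any event that developed post the blinded treatment period but was assessed by the Investigator as related to study treatment".

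The open-label paragraph of the same section has a parallel sentence, but there the causal agent is named as open-label selinexor. SAP 5.1.1.3 makes the same distinction for TRAEs: related to study treatment in general, and related to open-label selinexor for the open-label summaries.

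Other rules that decide where an event is counted:

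- **Relatedness.** The rule in SAP 5.1.2 begins "Based on the entries on the eCRF AE page, an AE is considered related to study treatment if the entry for" and goes on to name one field, the relationship to study treatment.
- **Population.** SAP 3.1.2 says that Ph3-SAF "will consist of all patients in Phase 3 who have received at least one dose of blinded study treatment"; Ph2-SAF is built the same way. It adds: "Patients in safety populations will be analyzed according to the actual treatment received".
- **Counting.** SAP 5.1.2: "The denominator for computation of percentages is the number of patients in the corresponding treatment arm", and "Multiple occurrences of the same event in the same patient will be counted only once in the tables".
- **Open-label period.** SAP 2.4, for patients randomized to placebo who cross over: "The open-label treatment period is defined as the time since the date of first open-label study treatment to the date of last open-label study treatment", plus 30 days.
- **Default.** SAP Section 5 restricts safety tables to blinded-period data unless otherwise specified, and presents selected open-label data for Ph3-OL and Ph2-OL separately.

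Protocol 14.3.6.1 also counts drug-related events through the end of the study, with no crossover cut-off.

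**The concern.** The base window has an explicit stop at crossover and the extension has none. A placebo patient who progresses may cross over to selinexor. At that point the Investigator is unblinded (Protocol 11.3.1) and assesses causality knowing which drug the patient is taking. A nausea or thrombocytopenia event attributed to that selinexor develops after the blinded period and is related to study treatment, so it meets both conditions of the extension.

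If the flag is programmed as written, events attributed to selinexor enter the placebo side of the blinded TEAE and TRAE tables, including serious and fatal TRAEs. For patients randomized to placebo the clause can add such events but cannot remove any. These are the tables a reader uses to compare the tolerability of the two arms.

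**Working it through.** The documents state no figure on this point, so there is nothing to reproduce. The check is a reading of the rules in sequence, then the weight of one patient.

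**Step 1: what time does the extension cover for a crossed-over placebo patient?** Under SAP 2.4 the blinded period ends 30 days after the last blinded dose or just before the first open-label dose, whichever comes first. Protocol 9.2 puts the EoBT visit within 14 days of the last blinded dose and open-label C1D1 within 14 days of that visit. The first open-label dose is therefore at most 14 + 14 = 28 days after the last blinded dose, inside the 30-day window. With compliant timing, everything after the blinded period is time from the first open-label dose onward. For these patients the extension reaches open-label time and later, and nothing else.

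**Step 2: does *study treatment* exclude open-label selinexor?** The general definition in SAP 2.3 covers selinexor or placebo without naming a phase. The SAP often adds *blinded* or *open-label* when it means one of them. The extension adds neither. The paragraph it sits in is about blinded summaries, which points to a narrower meaning but does not state one.

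**Step 3: does the relatedness field separate the phases?** SAP 5.1.2 describes one relationship field and shows no split. The eCRF itself is not in the documents.

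**Step 4: is the patient still in the blinded safety population?** Yes. One blinded dose is enough for Ph3-SAF or Ph2-SAF.

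**Step 5: which column?** Analysis by actual treatment is not divided by period. Placement under placebo follows from the membership rule; it is an inference, not a stated rule.

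**Step 6: does the blinded-only default remove the event?** It yields where something else is specified, and the extension is worded to bring in events after the blinded period.

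**Which events are affected.** The extension covers only events that developed after the blinded period. An event that began on placebo and later worsened is not brought in by it. Patients randomized to selinexor who continue open-label have their own rule: their period runs to 30 days after the last open-label dose. They are not affected.

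**Weight of one patient.** A repeat of the same event in a patient counts once, so a patient moves a percentage only if that event was not already counted for them in the blinded period.

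| Phase | Placebo n | Source | Points per newly affected patient |
|---|---|---|---|
| 3 | 285/3 = 95 | SAP 1.1, assuming exact 2:1 and all dosed | 100/95 = 1.05 |
| 3 (planned size) | 92 | Protocol synopsis | 100/92 = 1.09 |
| 2 | 30 | Protocol synopsis, assuming all dosed | 100/30 = 3.33 |

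A total would need the number who crossed over and the share of them with a related open-label event not already counted. Neither is given, so no total is computed.

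**The case against.** The strongest reply is that the paragraph should be read as a whole. It is introduced as applying to blinded summaries. Its open-label twin, and the twin in SAP 5.1.1.3, name open-label selinexor, so the natural pairing is blinded treatment against open-label selinexor. SAP 2.3 itself uses the unqualified term under separate blinded and open-label headings. SAP 2.4 makes open-label a distinct period, SAP 2.2.2 takes account of the selinexor start date for crossed-over patients when dates are partial, and Section 5 sends open-label data to separate summaries. Placing an event on selinexor in a placebo column also runs against analysis by treatment received. Finally, SAP 5.1.1.3 requires attribution to open-label selinexor, so the authors evidently thought it could be derived.

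Most of this stands as evidence of intent, and the literal result was probably not wanted. None of it is an exclusion, though. The same paragraph shows how a crossover cut-off is written, and the extension lacks one. Nor does the protocol supply it, since 14.3.6.1 is open-ended too. Whether the eCRF separates attribution by phase is unknown; the absence of a described split does not prove that none exists.

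A reader might infer that every such event is counted twice. The documents do not support that: Section 5 promises only selected open-label data, so an event may appear in both sets of tables but need not. A reader might also infer that the clause substantially masks the safety difference between the arms. That depends on crossover numbers and event rates in both arms, none of which is given.

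**Conclusion.** Wrong as written, of minor to moderate weight. Followed literally, the rule counts related events that first arise on open-label selinexor in patients randomized to placebo as blinded-period TEAEs and TRAEs. This rests on the unqualified reading of *study treatment*; placement in the placebo column rests further on the membership rule. The direction is known: placebo counts can only rise. The overall size is not known, and only the weight per newly affected patient can be stated.

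SAP Section 5 describes the safety analyses as essentially descriptive, with no systematic testing. The primary PFS analysis, the key secondary OS analyses and Type I error are not affected. The case for correcting it is that a stated rule gives a count its authors probably did not want, and a date condition settles the matter whichever reading was meant.

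**What to change.** After the extension sentence in SAP 5.1.1.1, add:

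*For patients randomized to placebo who enter open-label selinexor, this extension applies only to events with onset before the date of first open-label study treatment; events with onset on or after that date are not counted in the blinded-period summaries and are assessed under the open-label TEAE definition.*

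Three points on the wording:

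- It refers to onset only. Adding worsening could remove from the blinded tables an event that began on placebo. Such an event should stay there; its later worsening is already handled by the open-label definition.
- A date condition is safer than requiring attribution to blinded treatment, because the documents do not show that the eCRF records that split.
- The rule for patients randomized to selinexor who continue open-label stays as it is. SAP 5.1.1.3 needs no edit, because TRAEs are drawn from the TEAE set.

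Record the difference from Protocol 14.3.6.1 in SAP 1.7.

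The cost is one sentence, one entry in SAP 1.7 and one condition in the TEAE flag. The date needed is already defined in SAP 2.3: "For open-label treatment, the date of first study treatment is defined as the earliest date of non-zero dose of open-label selinexor". No new data are required.
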